7.1.2.1. Protocol-Specific Adverse Event Instructions

Anaphylaxis is a rare event that may occur after subcutaneous injections of monoclonal antibodies already approved for clinical use or those in clinical development such as GS-5745. In an effort to standardize the collection of adverse events that may comprise an anaphylactic event, in this study the definition developed by the National Institute of Allergy and Infectious Disease (NIAID)/Food Allergy and Anaphylaxis Network (FAAN) symposium will be utilized. Information reported by subjects regarding adverse events associated with the study drug will be collected and reviewed; the event causality will be assessed by the study investigator. If any of the AEs reported by the subject fulfill either Criteria 1 or Criteria 2 of the NIAID/FAAN definition of anaphylaxis (See [Appendix 11](#)) the event will be classified as anaphylaxis by the site investigator. The event will be considered medically significant and will be reported as an AE or SAE according to guidance in section [7.3](#). The medical monitor will be notified immediately. The subject may resume the study dosing in the discretion of investigator in consultation with the medical monitor for review and confirmation. Clinical Laboratory Abnormalities and Other Abnormal Assessments as Adverse Events or Serious Adverse Events

Laboratory abnormalities without clinical significance are not recorded as AEs or SAEs. However, laboratory abnormalities (eg, clinical chemistry, hematology, and urinalysis) that require medical or surgical intervention or lead to IMP interruption, modification, or discontinuation must be recorded as an AE, as well as an SAE, if applicable. In addition, laboratory or other abnormal assessments (eg, electrocardiogram, x-rays, vital signs) that are associated with signs and/or symptoms must be recorded as an AE or SAE if they meet the definition of an AE or SAE as described in Sections [7.1.1](#) and [7.1.2](#). If the laboratory abnormality is part of a syndrome, record the syndrome or diagnosis (eg, anemia), not the laboratory result (ie, decreased hemoglobin).

For specific information on handling of clinical laboratory abnormalities in this study, please refer to Section [7.5](#) and [7.6](#)

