7.2.2. Assessment of Severity

The severity of AEs will be graded using the CTCAE, version 4.03. For each episode, the highest grade attained should be reported.

If a CTCAE criterion does not exist, the investigator should use the grade or adjectives: Grade 1 (mild), Grade 2 (moderate), Grade 3 (severe), Grade 4 (life-threatening) or Grade 5 (fatal) to describe the maximum intensity of the adverse event. For purposes of consistency with the CTCAE, these intensity grades are defined in [Appendix 4](#).

7.3. Investigator Requirements and Instructions for Reporting Adverse Events and Serious Adverse Events to Gilead

Requirements for collection prior to study drug initiation:

After informed consent, but prior to initiation of study medication, the following types of events should be reported on the case report form (CRF/eCRF): all SAEs and adverse events related to protocol-mandated procedures.

Adverse Events

Following initiation of study medication, collect all AEs, regardless of cause or relationship, until 55-days after last administration of GS-5745 must be reported to the CRF/eCRF database as instructed.

All AEs should be followed up until resolution or until the adverse event is stable, if possible. Gilead Sciences may request that certain AEs be followed beyond the protocol defined follow up period.

Serious Adverse Events

All SAEs, regardless of cause or relationship, that occurs after the subject first consents to participate in the study (ie, signing the informed consent) and throughout the duration of the study, including the protocol-required post treatment follow-up period, must be reported to the CRF/eCRF database and Gilead Drug Safety and Public Health (DSPH) as instructed. This also includes any SAEs resulting from protocol-associated procedures performed after informed consent is signed.

Any SAEs and deaths that occur after the post treatment follow-up visit but within 55-days or of the last dose of study GS-5745, regardless of causality, should also be reported.

Investigators are not obligated to actively seek SAEs after the protocol defined follow up period, however, if the investigator learns of any SAEs that occur after study participation has concluded and the event is deemed relevant to the use of GS-5745, he/she should promptly document and report the event to Gilead DSPH.

- All AEs and SAEs will be recorded in the CRF/eCRF database within the timelines outlined in the CRF/eCRF completion guideline.

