Adverse events will be coded using the most recent version of the Medical Dictionary for Regulatory Activities (MedDRA). Severity should be recorded and graded according to the Common Terminology Criteria for Adverse Events (CTCAE) Version 4.03, which can be found at:

http://evs.nci.nih.gov/ftp1/CTCAE/CTCAE_4.03_2010-06-14_QuickReference_8.5x11.pdf

For adverse events associated with laboratory abnormalities, the event should be graded on the basis of the clinical severity in the context of the underlying conditions; this may or may not be in agreement with the grading of the laboratory abnormality.

7.6. **Toxicity Management**

- All clinical and clinically significant laboratory toxicities will be managed according to uniform guidelines detailed in [Appendix 3](#).
- Grade 3 and 4 clinically significant laboratory abnormalities should be confirmed by repeat testing within 3 calendar days of receipt of results and before investigational medicinal product discontinuation, unless such a delay is not consistent with good medical practice.
- Clinical events and clinically significant laboratory abnormalities will be graded according to the Common Terminology Criteria for Adverse Events (CTCAE) Version 4.03, which can be found at:
http://evs.nci.nih.gov/ftp1/CTCAE/CTCAE_4.03_2010-06-14_QuickReference_8.5x11.pdf
- When restarting investigational medicinal product following resolution of the adverse event, the investigational medicinal product should be restarted at full dose or modified dose that is dependent upon discussion with the Gilead Sciences Medical Monitor.
- Any recurrence of the investigational medicinal product-related Grade 3 or 4 clinical or clinically significant laboratory adverse event following dose interruption mandates permanent discontinuation of investigational medicinal product.
- Any questions regarding toxicity management should be directed to the Gilead Sciences Medical Monitor.

7.6.1. **Grades 1 and 2 Laboratory Abnormality or Clinical Event**

- Continue investigational medicinal product at the discretion of the investigator.

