7.6.2. Grades 3 Laboratory Abnormality or Clinical Event

- For Grade 3 clinically significant laboratory abnormality or clinical event, investigational medicinal product may be continued if the event is considered to be unrelated to investigational medicinal product.
- For a Grade 3 clinical event, or clinically significant laboratory abnormality confirmed by repeat testing, that is considered to be related to investigational medicinal product, investigational medicinal product should be withheld until the toxicity returns to \leq Grade 2.
- If a laboratory abnormality recurs to \geq Grade 3 following re-challenge with investigational medicinal product and is considered related to investigational medicinal product, then investigational medicinal product should be permanently discontinued and the subject managed according to local practice. Recurrence of laboratory abnormalities considered unrelated to investigational medicinal product may not require permanent discontinuation.

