7.6.3. Grade 4 Laboratory Abnormality or Clinical Event

- For a Grade 4 clinical event or clinically significant Grade 4 laboratory abnormality confirmed by repeat testing that is considered related to investigational medicinal product, investigational medicinal product should be permanently discontinued and the subject managed according to local practice. The subject should be followed as clinically indicated until the laboratory abnormality returns to Baseline or is otherwise explained, whichever occurs first. A clinically significant Grade 4 laboratory abnormality that is not confirmed by repeat testing should be managed according to the algorithm for the new toxicity grade.

Investigational medicinal product may be continued without dose interruption for a clinically non-significant Grade 4 laboratory abnormality (eg, Grade 4 CK after strenuous exercise or triglyceride elevation that is non-fasting or that can be medically managed) or a clinical event considered unrelated to investigational medicinal product.

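### Section 7.1.2.1 lets study drug be resumed after any anaphylaxis and does not except related Grade 4 events, for which Section 7.6.3 calls for permanent discontinuation

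*Protocol*

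**What the plan says.** Protocol Section 7.1.2.1 (Protocol-Specific Adverse Event Instructions) has the site investigator classify as anaphylaxis any event that meets Criterion 1 or 2 of Appendix 11. The investigator assesses causality and the medical monitor is told at once. On further dosing it says: "The subject may resume the study dosing in the discretion of investigator in consultation with the medical monitor for review and confirmation".

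Section 7.6 (Toxicity Management) sets the general rules: "All clinical and clinically significant laboratory toxicities will be managed according to uniform guidelines detailed in" Appendix 3. Its subsections then go by grade:

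- **Grades 1 and 2 (7.6.1):** "Continue investigational medicinal product at the discretion of the investigator".
- **Grade 3 (7.6.2):** drug may continue if the event is unrelated. If it is related, "investigational medicinal product should be withheld until the toxicity returns to" Grade 2 or lower.
- **Grade 4 (7.6.3):** the rule covers clinical events and clinically significant laboratory abnormalities, the latter being those "confirmed by repeat testing that is considered related to investigational medicinal product, investigational medicinal product should be permanently discontinued". Continuation is allowed only for a laboratory abnormality that is not clinically significant "or a clinical event considered unrelated to investigational medicinal product".

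**The concern.** The permission in 7.1.2.1 has no limit by grade or causality, although the same paragraph asks for a causality assessment. Section 7.6.3 leaves no room for discretion, or for confirmation by the monitor, once a Grade 4 clinical event is judged related. A life-threatening anaphylaxis attributed to study drug therefore meets two instructions that point in different directions.

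What is at stake is the safety of a subject who has just had such a reaction. A site that re-doses with the monitor's confirmation can say it followed the protocol's anaphylaxis instruction. Section 7.1.2.1 does not tell the site or the monitor that 7.6.3 limits the decision. Nor does it require the resumed dose to be given or observed at the site. Under Sections 3.3.2 and 5.3, capable subjects may self-inject at home after the first two doses, except on visit days.

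**Working it through.** The plan gives no figure to reproduce. The check sets the two rules side by side for every case that 7.1.2.1 covers, and then looks for text that reconciles them.

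**Can an Appendix 11 event be Grade 4?** The criteria include reduced blood pressure with collapse or syncope, and respiratory compromise. Section 7.2.2 and Appendix 4 define Grade 4 as life-threatening. The documents show no grading specific to anaphylaxis, so nothing confines it to lower grades. The overlap is possible.

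**Which cases conflict?** Section 7.2.2 gives five grades. Grade 5 is fatal, so resumption does not arise and four grades remain. Section 7.2.1 gives two causality answers, No and Yes. The number of combinations is 4 × 2 = 8.

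| Grade | Related? | Combinations | 7.1.2.1 | 7.6.1 to 7.6.3 | Conflict? |
|---|---|---|---|---|---|
| 1 or 2 | No or Yes | 4 | May resume | Continue at investigator discretion | No |
| 3 | No | 1 | May resume | May continue | No |
| 3 | Yes | 1 | May resume | Withhold to Grade 2 or lower; restart then possible | No |
| 4 | No | 1 | May resume | May continue | No |
| 4 | Yes | 1 | May resume | Permanent discontinuation | **Yes** |

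No conflict: 4 + 1 + 1 + 1 = 7. Conflict: 1 of 8. If anaphylaxis is assumed always to be Grade 3 or 4, the table shrinks to 2 × 2 = 4 combinations, and the conflict is 1 of 4.

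**Does other text settle the eighth case?**

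- *Section 7.6, scope.* It covers all clinical toxicities and carves out no exception for anaphylaxis. This favours stopping, but it does not say that it limits 7.1.2.1.
- *Section 7.6, recurrence.* "Any recurrence of the investigational medicinal product-related Grade 3 or 4 clinical or clinically significant laboratory adverse event following dose interruption mandates permanent discontinuation". This may concern only a Grade 3 event that was interrupted and came back. Because it also names Grade 4, it can be read as allowing a restart after a first related Grade 4 event. It does not decide the matter.
- *Section 3.5.2.* The list of reasons to stop permanently names neither anaphylaxis nor Grade 4 events. Unacceptable toxicity is listed separately from the clause on investigator judgment, but it is not defined.
- *Exclusion criterion 4 with Section 6.1.* Known hypersensitivity to the drug is exclusionary, and the investigator is to ensure eligibility during the study as well as at entry. Together they point to stopping, but only by inference.
- *Cross-references.* The only pointer from 7.1.2.1 to 7.6 concerns laboratory abnormalities.
- *Appendix 3.* Only its title can be read, so whether it addresses anaphylaxis cannot be checked.

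**The case against.** The strongest reply is that a permission in one section and a restriction in another normally apply together. Section 7.1.2.1 sits under definitions, and its stated aim is to standardise how anaphylaxis is collected. Section 7.6 is where toxicity is managed, and 7.6.3 addresses Grade 4 clinical events directly. On this reading 7.6.3 governs, and a site can always comply with both sections by stopping. Resumption is also not automatic: the medical monitor must review and confirm it, and 7.6 makes the monitor the contact for questions on toxicity management. The laboratory cross-reference closes what looks like a separate laboratory block, so its silence on anaphylaxis shows little. Section 7.6.3 says should rather than must, and Appendix 3 might settle the matter.

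Most of this stands as far as it goes. Reading 7.6.3 as the limit is reasonable and probably safer, the monitor is a real safeguard, and the cross-reference carries little weight. But the opposite reading is also open. Section 7.1.2.1 is headed as protocol-specific instruction, and a site may take the rule written for anaphylaxis to displace the general one. One rule is specific by diagnosis and the other by grade and causality, so neither is plainly the narrower. The unreadable appendix cannot be counted for either side. What remains is an express permission to re-dose in a case where another section says to stop, with no readable statement of which prevails.

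**Conclusion.** The concern holds. The permission in 7.1.2.1 is too broad by one case: Grade 4 anaphylaxis considered related to study drug. That is 1 of 8 rule combinations, or 1 of 4 under the assumption that only Grades 3 and 4 occur. Neither count is a probability, and the protocol gives no anaphylaxis rate. No estimate, test or sample size is affected.

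The conclusion rests on two conditions: that anaphylaxis can be graded 4, which the Appendix 11 criteria support, and that Appendix 3, which cannot be read here, does not already contain the limit. Confidence is moderate for that second reason. The correction should be made because the case is life-threatening and the change is small. SAP Section 1 records that the sponsor terminated the study on 5 June 2017, which limits the practical benefit in this trial but does not make the protocol text consistent.

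**What to change.** Add to the end of the resumption sentence in 7.1.2.1: *except after Grade 4 anaphylaxis considered related to study drug, for which Section 7.6.3 applies and study drug is permanently discontinued*. A matching bullet in 3.5.2 would help sites that look there first, but is optional. No Grade 3 clause is needed, because 7.6.2 already applies without conflict.

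The cost is one clause of protocol text. Visits, sample size and analysis stay as they are.

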7.2. Assessment of Adverse Events and Serious Adverse Events

The investigator or qualified sub investigator is responsible for assessing AEs and SAEs for causality and severity, and for final review and confirmation of accuracy of event information and assessments.

7.2.1. Assessment of Causality for Study Drugs and Procedures

The investigator or qualified sub investigator is responsible for assessing the relationship to IMP therapy using clinical judgment and the following considerations:

- **No:** Evidence exists that the adverse event has an etiology that is more likely than the IMP. For SAEs, an alternative causality must be provided (eg, pre-existing condition, underlying disease, intercurrent illness, or concomitant medication).
- **Yes:** There is reasonable possibility that the event may have been caused by the investigational medicinal product.

It should be emphasized that ineffective treatment should not be considered as causally related in the context of adverse event reporting.

The relationship to study procedures (eg, invasive procedures such as venipuncture or biopsy) should be assessed using the following considerations:

- No evidence exists that the adverse event has an etiology other than the study procedure.
- **Yes:** The adverse event occurred as a result of protocol procedures, (eg venipuncture)

7.2.2. Assessment of Severity

The severity of AEs will be graded using the CTCAE, version 4.03. For each episode, the highest grade attained should be reported.

If a CTCAE criterion does not exist, the investigator should use the grade or adjectives: Grade 1 (mild), Grade 2 (moderate), Grade 3 (severe), Grade 4 (life-threatening) or Grade 5 (fatal) to describe the maximum intensity of the adverse event. For purposes of consistency with the CTCAE, these intensity grades are defined in [Appendix 4](#).

7.3. Investigator Requirements and Instructions for Reporting Adverse Events and Serious Adverse Events to Gilead

Requirements for collection prior to study drug initiation:

After informed consent, but prior to initiation of study medication, the following types of events should be reported on the case report form (CRF/eCRF): all SAEs and adverse events related to protocol-mandated procedures.

Adverse Events

Following initiation of study medication, collect all AEs, regardless of cause or relationship, until 55-days after last administration of GS-5745 must be reported to the CRF/eCRF database as instructed.

All AEs should be followed up until resolution or until the adverse event is stable, if possible. Gilead Sciences may request that certain AEs be followed beyond the protocol defined follow up period.

Serious Adverse Events

All SAEs, regardless of cause or relationship, that occurs after the subject first consents to participate in the study (ie, signing the informed consent) and throughout the duration of the study, including the protocol-required post treatment follow-up period, must be reported to the CRF/eCRF database and Gilead Drug Safety and Public Health (DSPH) as instructed. This also includes any SAEs resulting from protocol-associated procedures performed after informed consent is signed.

Any SAEs and deaths that occur after the post treatment follow-up visit but within 55-days or of the last dose of study GS-5745, regardless of causality, should also be reported.

Investigators are not obligated to actively seek SAEs after the protocol defined follow up period, however, if the investigator learns of any SAEs that occur after study participation has concluded and the event is deemed relevant to the use of GS-5745, he/she should promptly document and report the event to Gilead DSPH.

- All AEs and SAEs will be recorded in the CRF/eCRF database within the timelines outlined in the CRF/eCRF completion guideline.
- At the time of study start, SAEs may be reported using a paper serious adverse event reporting form. During the study conduct, sites may transition to an electronic SAE (eSAE) system. Gilead will notify sites in writing and provide training and account information prior to implementing an eSAE system.

Electronic Serious Adverse Event (eSAE) Reporting Process

- Site personnel record all SAE data in the eCRF database and from there transmit the SAE information to Gilead DSPH within 24 hours of the investigator's knowledge of the event. Detailed instructions can be found in the eCRF completion guidelines.
- If for any reason it is not possible to record the SAE information electronically, ie, the eCRF database is not functioning, record the SAE on the paper serious adverse event reporting form and submit within 24 hours to:

Gilead DSPH : [contact]
E-mail: [contact]

- As soon as it is possible to do so, any SAE reported via paper must be transcribed into the eCRF Database according to instructions in the eCRF completion guidelines.
- If an SAE has been reported via a paper form because the eCRF database has been locked, no further action is necessary.
- For fatal or life-threatening events, copies of hospital case reports, autopsy reports, and other documents are also to be submitted by e-mail or fax when requested and applicable. Transmission of such documents should occur without personal subject identification, maintaining the traceability of a document to the subject identifiers.
- Additional information may be requested to ensure the timely completion of accurate safety reports.
- Any medications necessary for treatment of the SAE must be recorded onto the concomitant medication section of the subject's CRF/eCRF and the event description section of the SAE form.

7.4. Gilead Reporting Requirements

Depending on relevant local legislation or regulations, including the applicable US FDA Code of Federal Regulations, the EU Clinical Trials Directive (2001/20/EC) and relevant updates, and other country-specific legislation or regulations, Gilead may be required to expedite to worldwide regulatory agencies reports of SAEs, serious adverse drug reactions (SADRs), or suspected unexpected serious adverse reactions (SUSARs). In accordance with the EU Clinical Trials Directive (2001/20/EC), Gilead or a specified designee will notify worldwide regulatory agencies and the relevant IEC in concerned Member States of applicable SUSARs as outlined in current regulations.

Assessment of expectedness for SAEs will be determined by Gilead using reference safety information specified in the investigator's brochure.

Any SAEs that are attributed to background RA medication (subject's TNF inhibitor or MTX) by the investigator will be forwarded to the relevant marketing authorization holder.

All investigators will receive a safety letter notifying them of relevant SUSAR reports associated with any study IMP. The investigator should notify the IRB or IEC of SUSAR reports as soon as is practical, where this is required by local regulatory agencies, and in accordance with the local institutional policy.

7.5. Clinical Laboratory Abnormalities and Other Abnormal Assessments as Adverse Events or Serious Adverse Events

Laboratory abnormalities are usually not recorded as AEs or SAEs. However, laboratory abnormalities (eg, clinical chemistry, hematology, urinalysis) independent of the underlying medical condition that require medical or surgical intervention or lead to investigational

medicinal product interruption or discontinuation must be recorded as an AE, as well as an SAE, if applicable. In addition, laboratory or other abnormal assessments (eg, electrocardiogram, X-rays, vital signs) that are associated with signs and/or symptoms must be recorded as an AE or SAE if they meet the definition of an AE (or SAE) as described in Sections 7.1.1 and 7.1.2. If the laboratory abnormality is part of a syndrome, record the syndrome or diagnosis (ie, anemia) not the laboratory result (ie, decreased hemoglobin).

Adverse events will be coded using the most recent version of the Medical Dictionary for Regulatory Activities (MedDRA). Severity should be recorded and graded according to the Common Terminology Criteria for Adverse Events (CTCAE) Version 4.03, which can be found at:

http://evs.nci.nih.gov/ftp1/CTCAE/CTCAE_4.03_2010-06-14_QuickReference_8.5x11.pdf

For adverse events associated with laboratory abnormalities, the event should be graded on the basis of the clinical severity in the context of the underlying conditions; this may or may not be in agreement with the grading of the laboratory abnormality.

7.6. **Toxicity Management**

- All clinical and clinically significant laboratory toxicities will be managed according to uniform guidelines detailed in [Appendix 3](#).
- Grade 3 and 4 clinically significant laboratory abnormalities should be confirmed by repeat testing within 3 calendar days of receipt of results and before investigational medicinal product discontinuation, unless such a delay is not consistent with good medical practice.
- Clinical events and clinically significant laboratory abnormalities will be graded according to the Common Terminology Criteria for Adverse Events (CTCAE) Version 4.03, which can be found at:
http://evs.nci.nih.gov/ftp1/CTCAE/CTCAE_4.03_2010-06-14_QuickReference_8.5x11.pdf
- When restarting investigational medicinal product following resolution of the adverse event, the investigational medicinal product should be restarted at full dose or modified dose that is dependent upon discussion with the Gilead Sciences Medical Monitor.
- Any recurrence of the investigational medicinal product-related Grade 3 or 4 clinical or clinically significant laboratory adverse event following dose interruption mandates permanent discontinuation of investigational medicinal product.
- Any questions regarding toxicity management should be directed to the Gilead Sciences Medical Monitor.

7.6.1. **Grades 1 and 2 Laboratory Abnormality or Clinical Event**

- Continue investigational medicinal product at the discretion of the investigator.

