3.5. Study Subject Interruption and Discontinuation Criteria

3.5.1. Study drug interruption considerations:

The Medical Monitor should be consulted prior to study drug interruption when medically feasible.

Study drug interruption should be considered in the following circumstances; *prior to resumption of study drug, the investigator should discuss the case with the Gilead medical monitor:*

- Intercurrent illness that would, in the judgment of the investigator, affect assessments of clinical status to a significant degree.
- Subject is scheduled for elective or emergency surgery (excluding minor skin procedures under local or no anesthesia); timing of study drug pausing should be determined in consultation with the Gilead medical monitor.
- Any subject who develops a new infection during the study should undergo prompt and complete diagnostic testing appropriate for an immunocompromised individual, and the subject should be closely monitored.

NOTE: During the time of study drug interruption for any of the above, the subject may continue to have study visits and to take part in procedures and assessments, if deemed medically appropriate by the investigator.

3.5.2. Study drug discontinuation considerations:

The Medical Monitor should be consulted prior to study drug discontinuation when medically feasible.

Study medication should be permanently discontinued in the following instances:

- Any opportunistic infection
- Any **serious** infection that requires antimicrobial therapy or hospitalization, or any infection that meets SAE reporting criteria
- Complicated herpes zoster infection (with multi-dermatomal, disseminated, ophthalmic, or CNS involvement)
- Evidence of active HBV during study, as evidenced by HBV DNA positivity

- Evidence of active HCV during the study, as evidenced by HCV RNA positivity
- Unacceptable toxicity, or toxicity that, in the judgment of the investigator, compromises the subject's ability to continue study specific procedures or is considered to not be in the subject's best interest
- Subject request to discontinue for any reason
- Subject noncompliance
- Pregnancy during the study ([Appendix 5](#))
- Discontinuation of the study at the request of Gilead, a regulatory agency or an institutional review board or independent ethics committee
- Subject use of prohibited concurrent therapy may trigger study drug discontinuation: consultation should be made with the Gilead medical monitor

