##### 7.1.6.1. Summaries of AE incidence in Combined Severity Grade Subsets

For TEAEs described below, summaries will be provided by SOC, PT, treatment group, and study phase:

- All TE treatment-related AEs
- All TE SAEs
- All TEAEs leading to premature discontinuation of study drug
- TEAEs of interest:
  - injection site reactions (based on Gilead medical search terms provided by DSPH)

A brief, high-level summary of AEs described above will also be provided by treatment group and study phase.

In addition to the above summary tables, all TEAEs will be summarized by PT only, in descending order of total frequency. Summaries of all TEAEs by SOC, PT, and maximum severity will also be provided.

Multiple events will be counted only once per subject in each summary. Adverse events will be summarized and listed first in alphabetic order of SOC and PT in descending order of total frequency within each SOC. For summaries by severity grade, the most severe grade will be used for those AEs that occurred more than once in an individual subject during the study.

In addition, data listings will be provided for the following:

- All AEs, indicating whether the event is treatment-emergent
- SAEs
- Deaths
- AEs leading to premature discontinuation of study drug

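### Protocol 7.1.2.1 and 7.5 set different triggers for recording a laboratory abnormality as an AE: one attributed to RA that interrupts or stops study drug must be recorded under the first but not under the second

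*Protocol*

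**What the plan says.** Protocol 7.1.2.1, in the text after the anaphylaxis instructions, starts from a narrow exclusion: "Laboratory abnormalities without clinical significance are not recorded as AEs or SAEs". It then makes recording mandatory for laboratory abnormalities "that require medical or surgical intervention or lead to IMP interruption, modification, or discontinuation must be recorded as an AE". Cause plays no part. The section ends with a pointer to 7.5 and 7.6: "For specific information on handling of clinical laboratory abnormalities in this study, please refer to Section".

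Protocol 7.5 starts from a wider exclusion: "Laboratory abnormalities are usually not recorded as AEs or SAEs". Its mandatory rule covers only abnormalities "independent of the underlying medical condition that require medical or surgical intervention or lead to investigational", and the sentence continues "medicinal product interruption or discontinuation must be recorded as an AE, as well as an SAE, if applicable". Dose modification is not in that list.

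Both sections share two further rules. Abnormal results with signs or symptoms are recorded if they meet the AE definition, and a syndrome or diagnosis is recorded in place of the laboratory value.

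SAP 7.1.6.1 tabulates, by treatment group, "All TEAEs leading to premature discontinuation of study drug". SAP 7.1.5.1, like protocol 8.6.2, counts any AE that led to early discontinuation of study drug as treatment-emergent.

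**The concern.** Every subject in this trial has active RA, so attributing a laboratory change to the underlying disease is always open to the investigator. Under 7.5 that attribution decides whether an AE record is required at all. Under 7.1.2.1 it does not. A site is sent from one text to the other with no statement of precedence, so two sites can treat the same event differently and each can point to the protocol.

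The events affected are those that changed treatment. An event not entered as an AE cannot appear in the TEAE summaries or among the TEAEs that ended study drug early. Safety and tolerability is a secondary objective. A judgement on cause belongs in the relatedness field, where a reader can see it. Used as an entry condition, it removes the event before anyone can assess it. The SAP's conservative handling of missing relatedness, which counts such events as related (SAP 7.1.3), cannot help an event that was never entered.

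**Working it through.** The plan states no figure on this point, so the check is a comparison of the two texts followed by simple arithmetic on the size of one event.

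**Step 1. The two rules side by side**

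| Element | Protocol 7.1.2.1 | Protocol 7.5 |
|---|---|---|
| Not recorded by default | abnormalities lacking clinical significance | abnormalities in general, as the usual case |
| Condition on cause | none | must be independent of the underlying condition |
| Medical or surgical intervention | trigger | trigger |
| Interruption of study drug | trigger | trigger |
| Discontinuation of study drug | trigger | trigger |
| Modification of study drug | trigger | not listed |
| Which text prevails | not stated | not stated |

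**Step 2. Outcome by case**

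- (a) The abnormality needs intervention, or interrupts or stops study drug, and is independent of the underlying condition. Both sections require an AE record, so there is no conflict.
- (b) It has the same consequence but is attributed to the underlying condition. Section 7.1.2.1 requires an AE record and 7.5 does not. This is the conflict.
- (c) It leads only to a dose modification. The texts differ, but 7.6 mentions a modified dose only when study drug is restarted after an event has resolved. On that route an interruption, which 7.5 lists, has already occurred, so this difference matters little in practice.

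**Step 3. Which case (b) events are exposed**

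- Protocol 7.1.1 counts a pre-existing event that worsens or changes character as an AE, and 7.3 requires all AEs to be collected whatever their cause. Many case (b) events enter by this route.
- Results with signs or symptoms that meet the AE definition are recorded under both sections.
- What remains is a condition-attributed abnormality that the site does not regard as a worsening or otherwise as an AE, where the site relies on 7.5 alone.

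**Step 4. Size of one lost event**

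- Planned arms: 25 subjects (protocol 3.3 and 8.9). 1/25 = 4.0 percentage points.
- Enrolled: 15 subjects in total (SAP 1.3). The split by arm is not given. Assuming an even split, 15/3 = 5 per arm and 1/5 = 20 points. Assuming arms of 4 to 6, the range is 1/6 = 16.7 to 1/4 = 25 points.
- Rate of such events: not given in the documents, so no expected count is calculated.

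**The case against.** The strongest reply is that 7.5 sets a floor and prohibits nothing. A site that records under 7.1.2.1 complies with both sections, and under-recording requires it to overlook a mandatory sentence. Sections 7.1.1 and 7.3 stand behind both. This is largely right and limits the reach of the point. It does not remove it: 7.1.2.1 itself refers the site to 7.5 for specifics, and the restricted wording there is easily taken as the operative rule.

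The qualifier in 7.5 could also be read as meaning regardless of the underlying condition, which would remove case (b). In the sentence it qualifies the abnormalities themselves, so a restriction is the more natural reading. Wording that can be read both ways still needs repair.

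Three stronger inferences are tempting, and the documents do not support them.

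- A reader might infer that any abnormality that stops study drug can escape AE recording. Both sections require a record whenever the abnormality is independent of the underlying condition.
- A reader might take hepatitis B as the clearest example, because protocol 3.5.2 lists "Evidence of active HBV during study, as evidenced by HBV DNA positivity" among the reasons for permanent discontinuation. The underlying condition in this trial is RA, and viral DNA positivity is independent of it, so 7.5 requires the record as well. Extending the phrase to prior viral exposure goes beyond the text.
- A reader might infer that the AE tables are the only trace of such an event. The SAP drops descriptive laboratory statistics (7.2.1) but keeps treatment-emergent graded abnormalities by arm and a listing of Grade 3 or higher (7.2.2.2), flagged hematology and chemistry listings (7.2), reasons for stopping study drug (4.1) and a dosing listing (4.2.2). With 15 subjects, these can help to trace a laboratory-driven stop.

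It is also fair to say that the study was terminated on 5 June 2017 and that no inferential analysis is planned. Rewording the protocol cannot change data already collected.

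**Conclusion.** The two sections state different mandatory triggers and must be reconciled. The conflict that matters is confined to abnormalities attributed to the underlying condition that need intervention or lead to interruption or discontinuation. The missing modification trigger and the different defaults are secondary.

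The consequence is limited to events of that kind that a site following 7.5 does not enter as an AE. They then drop out of the TEAE table and the table of TEAEs leading to discontinuation, although the laboratory value and the dosing record remain. One such event is worth 4 points in a planned arm and about 20 points in an arm of 5, the latter resting on an assumed even split. Nothing in the documents shows that an event was lost, and they give no rate from which to estimate how many could be.

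The correction is still worth making. It is cheap, and it takes a judgement on cause out of the entry condition for a safety table. For this terminated study only the data query can affect what is reported; the rewording serves any later use of the protocol text.

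**What to change.** **Protocol text.** Use one recording rule in both sections. In 7.5, delete the first six words of "independent of the underlying medical condition that require medical or surgical intervention or lead to investigational", and match the list of triggers and the default sentence to 7.1.2.1. Keep attribution in the relatedness field. This concerns recording only and alters no dosing or stopping rule.

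**Synoptic CSR.** Before data finalization, compare the dosing listing and the reasons for stopping study drug with the AE data for the 15 subjects. Query any interruption or discontinuation made for a laboratory reason that has no matching AE. SAP 2.2 already places the final analysis after outstanding queries are resolved, so this fits the existing sequence.

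**Cost.** A short edit to one section and one query over 15 subjects. The downside is that a few RA-related laboratory events may be added to the AE tables, where their attribution will be visible.
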